- The Stroke and Aphasia Quality of Life Scale,^{157,158} Stroke Impact Scale,¹³⁸ EQ-5D and Patient Health Questionnaire¹⁴⁷ are reliable and valid self-report quantitative surveys that include questions about quality of life. One or more of these questionnaires will be used.
- The Global Rating of Change (GROC)¹⁵⁹ is a questionnaire that assesses overall impressions of change in health status from the perspective of the participant. The GROC is a 15 point ordinal scale with -7 indicating "a very great deal worse," 0 indicating "no change," and +7 indicating "a very great deal better". The GROC is not applicable at baseline testing because it measures change only.

Heart rate data may also be recorded during the above testing. If there are any issues with data capture (e.g. equipment malfunction), it is possible that participants could be asked to repeat individual tests as long as it would still be possible to obtain quality data without increasing risk to the participant.

Randomization

Participants will be enrolled after PRE testing and randomized to either HIT or MAT. Randomization will be stratified by site and by baseline walking speed (<0.4 , ≥ 0.4 m/s), to help ensure that groups are balanced within sites and on this critical prognostic factor.^{149,150} Within each stratum, we will randomize in *block sizes of 2 or 4*. Block size will be *randomly permuted* to prevent personnel from being able to predict the last randomization within a block.

Training Intervention Protocols

Common features between protocols. Participants in both groups will be asked to perform 36 training sessions over approximately 12 weeks, with repeated outcome testing after each [12 session / 4 week] block. Target training frequency will be 3 sessions per week. Both groups will train for approximately 45 minutes per session, v.5, 16Mar2021

using orthotic & assistive devices and handrail balance support on the treadmill as needed.¹⁴⁴ Each session will include a 3 minute warm up, 10 min overground training with guarding from a physical therapist, 20 min treadmill training wearing a harness for fall protection, another 10 min overground training and a 2 min cool down. Target heart rates (HRs) will be based on the peak HR from exercise testing, to account for β -blocker medications.¹⁴⁴

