Locomotor high-intensity interval training (HIT). This protocol was developed and refined in our preliminary studies. It involves repeated bursts of walking at speeds up to the participant's fastest safe speed, alternated with recovery periods of slower walking or rest. During overground HIT, burst speed is increased using visual feedback about the distance covered during each burst and encouragement to increase distance. During treadmill HIT, speed is systematically progressed throughout each session based on participant performance criteria and heart rate response.^{9,81,82} Target average HR for each session is approximately 85% HR_{peak} (~70% HR reserve [HRR]).

Locomotor moderate-intensity aerobic training (MAT). Similar to our pilot randomized controlled trial,⁹ this protocol will follow the widely reported training regimen of Macko et al,^{33,46,50,51,60-62,144,215,216} used as the basis for current post-stroke exercise guidelines.^{6,8} The only adjustment for this study will be the addition of overground MAT¹⁰⁹ to match the training modes and duration of locomotor HIT. During both treadmill and overground MAT, speed will be continuously adjusted to maintain an initial target HR of 40 \pm 5% heart rate reserve (HRR), progressing by 5% HRR every 2 weeks up to 60% HRR, as tolerated.¹⁴⁴

[figure not shown]
Intervention fidelity measures

Integrity of the training protocol may be assessed by the following measures:

- Adherence will be measured by the number of training sessions attended
- Aerobic intensity will be measured by training heart rates. Heart rate data may be collected by a heart rate transmitter worn around the chest (e.g. Polar H7), an ECG, a pulse oximeter and/or manual palpation. Heart rate data may be processed using an iPod (or similar) application (e.g. FitDigits iCardio).

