- Anaerobic intensity may be measured by *blood lactate concentration* after the treadmill training portion of one or more sessions, using a finger stick and a point-of-care blood lactate analyzer. Blood lactate accumulation is a key feature of vigorous training intensity that provides a mechanistic basis for expected benefits over moderate intensity. Our preliminary data confirmed that among persons with chronic stroke, the anaerobic threshold still occurs almost exactly at the 60% HR reserve transition point between moderate and vigorous intensity.¹³⁶ Further, we demonstrated that our treadmill HIT protocol elicits a consistent and robust lactate response in this population, which is significantly greater than the null effect elicited by MAT ($p<0.001$; Fig 5). In animal and healthy adult studies, increased blood lactate has been shown to drive skeletal muscle mitochondrial adaptations that increase aerobic capacity,¹⁶⁶ to upregulate neurotrophins that facilitate brain plasticity¹⁶⁷ and to predict greater motor learning when paired with skill practice.¹⁶⁸
- Neuromotor intensity may be measured by *treadmill and over ground training speeds* each session.
- Repetition of practice may be measured by *step counts* during each session, using an activity monitor on the non-paretic leg.^{27,34,35,169,170}

Concurrent outside interventions

To test for other between-group differences during the intervention period that could explain differences in outcomes, we may also assess the following measures:

- Concurrent walking practice may be measured by *step counts outside of training sessions*. Participants would be asked to take an activity monitor home to wear during waking hours throughout study participation.¹⁷¹
- Concurrent therapy may be measured by *any changes in medications* and the *number of sessions of outside therapy (e.g. speech & occupational therapy)*.¹⁵⁶

E.2. Data Analysis and Data Monitoring

General approach

[figure not shown]
The REDCap® web-based system²¹⁷ will be used for data entry and data monitoring. All baseline variables and data on intervention fidelity and concurrent outside interventions will be compared between groups with t-tests and X². The primary analysis will follow *intent-to-treat* methods and any missing data will be handled with the method of maximum likelihood, assuming that patterns of missingness do not violate the missing at random assumption.²¹⁸

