H_{1a} will be tested by the significance of the [group x time] contrast from Baseline to POST-4wk for the 6-minute walk test at $\alpha=0.05$. For H_{1b}, secondary outcomes will be tested separately using the same model as H_{1a} to identify the most sensitive measures to carry forward into future studies.¹¹⁰ The Benjamini-Hochberg procedure²²³ will be used to control the false discovery rate (FDR) for the secondary outcomes.

Aim 2: Determine the minimum locomotor training duration needed to maximize immediate effects

Hypothesis 2a (H_{2a}): Within the HIT group, *walking capacity* (6 minute walk test distance) and *secondary outcomes* will significantly increase from 4WK to 8WK and from 8WK to 12WK

Hypothesis 2b (H_{2b}): Compared to MAT, HIT will elicit significantly greater improvements in *walking capacity* and *secondary outcomes* from PRE to 8WK and from PRE to 12WK

H_{2a} will be tested by the significance of the respective time contrasts within the HIT group. **H_{2b}** will be tested by the significance of the respective [group x time] contrasts. Secondary outcomes will have FDR control.²²³

Data and Safety Monitoring Plan

An adverse event (AE) is an undesired medical occurrence in a participant who is undergoing study procedures and does not necessarily have a causal relationship with the treatment or study procedures. This includes any adverse clinical change that occurs at any time following consent. A serious AE (SAE) is any adverse experience occurring during study participation that results in any of the following outcomes: death; a life threatening situation; inpatient hospitalization or prolongation of existing hospitalization; a persistent or significant disability/incapacity.^{209,210} The data and safety monitoring plan for this study will include participant monitoring for AEs and other problems, review of AEs and other problems by the study team and IRB, and an independent data safety monitoring board (DSMB).

Participant safety monitoring

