The DSMB will consist of at least 3 members separate from the study team, including at least one physician and at least one biostatistician, with collective experience in the management of patients with stroke, exercise and clinical trials. A quorum will require at least 2 members, including the chair. Persons with a significant conflict of interest (financial, institutional or scientific) will not be permitted to be DSMB members. The DSMB will meet at least (approximately) annually. A summary report will be sent to the DSMB prior to each meeting, including safety and clinical outcome data. DSMB meetings will include open sessions where the DSMB may discuss any issues with the study team and closed sessions where the DSMB alone decides on its recommendations. The DSMB will assess the risks and benefits of study participation for all participants and will provide a written report of their analyses and recommendation as to whether the study should continue, whether modifications to the study are needed or if the study should be terminated. These reports will be sent to the investigators and the IRB.

Safety Data Analysis

In the unexpected event of one or more SAEs, the SAE rate will be compared between groups to confirm that there is no significant difference in major safety risk between HIT and MAT. This analysis will use a logistic regression model with SAE (yes/no) as the dependent variable and fixed effects for group, site and baseline gait speed category. If there are SAE(s) in one group only, a continuity correction (0.5 SAEs added to each group) will still allow the odds ratio to be calculated.⁹ Secondary safety outcomes (different grades/categories of AEs) will be tested using the same model, with [# AEs / # training sessions] as the dependent variable.⁹

E.3. Data Storage and Confidentiality

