Table 7. Adverse Events (AEs) in Pilot RCT

Data reported as no. of participants with AE (total no. of AEs) [AE incidence rate per 100 sessions]

	HIT (n=13, sessions=141)	MAT (n=5, sessions=60)	HIT/MAT AE odds ratio (95% CI)
Any AE	9 (21) [14.9]	4 (8) [13.3]	1.14 (0.47-2.73)
Related to intervention	6 (13) [9.2]	1 (4) [6.7]	1.42 (0.44-4.55)
-Grade 1 (mild)	5 (10) [7.1]	1 (3) [5.0]	1.45 (0.38-5.47)
-Grade 2 (moderate)	2 (3) [2.1]	1 (1) [1.7]	1.28 (0.13-12.59)
-Grade 3-5 (severe-death)	0 (0) [0.0]	0 (0) [0.0]	N/A
-Cardiac disorder	0 (0) [0.0]	0 (0) [0.0]	N/A
-Joint/muscle pain	5 (8) [5.7]	1 (4) [6.7]	0.84 (0.24-2.91)
-Fatigue	3 (3) [2.1]	0 (0) [0.0]	3.03 (0.15-59.56)*
-Nausea	0 (0) [0.0]	0 (0) [0.0]	N/A
-Lightheadedness	1 (2) [1.4]	0 (0) [0.0]	2.15 (0.10-45.43)*
-Other nervous system	0 (0) [0.0]	0 (0) [0.0]	N/A
-Fall	0 (0) [0.0]	0 (0) [0.0]	N/A
-Other injury	0 (0) [0.0]	0 (0) [0.0]	N/A
Unrelated to intervention	6 (8) [5.7]	3 (4) [6.7]	0.84 (0.24-2.91)
-Grade 1 (mild)	5 (7) [5.0]	2 (2) [3.3]	1.51 (0.31-7.51)
-Grade 2 (moderate)	1 (1) [0.7]	2 (2) [3.3]	0.21 (0.02-2.33)
-Grade 3-5 (severe-death)	0 (0) [0.0]	0 (0) [0.0]	N/A
-Atrial fibrillation	1 (2) [1.4]	0 (0) [0.0]	2.15 (0.10-45.43)*
-Other cardiac disorder	0 (0) [0.0]	0 (0) [0.0]	N/A
-Joint/muscle pain	2 (2) [1.4]	1 (2) [3.3]	0.42 (0.06-3.03)
-Fatigue	1 (1) [0.7]	0 (0) [0.0]	1.28 (0.05-31.86)*
-Nausea	0 (0) [0.0]	0 (0) [0.0]	N/A
-Lightheadedness	1 (1) [0.7]	0 (0) [0.0]	1.28 (0.05-31.86)*
-Other nervous system	0 (0) [0.0]	0 (0) [0.0]	N/A
-Fall	1 (1) [0.7]	2 (2) [3.3]	0.21 (0.02-2.33)
-Other injury	1 (1) [0.7]	0 (0) [0.0]	1.28 (0.05-31.86)*

AE odds ratios are from logistic regression modeling of no. of AEs / no. of sessions per participant. CI, confidence interval. *Continuity corrected by adding 0.5 AEs to each group so that AE odds ratios could be calculated. HIT, high-intensity interval training; MAT, moderate-intensity aerobic training

Emergency Response Planning. Although we expect that the study will be safe, we are also well prepared for any unlikely events. AEs will be promptly reported to the IRB and DSMB (see Data and Safety Monitoring Plan above) and referrals for follow up care will be made according to the severity and type of event. Should an emergency medical situation occur during study activities, emergency medical care would be provided and the participant would be transported to the nearest emergency room.

G.2. Potential Benefits

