Statistical Analysis Plan

NCT03760016

Moderate-Intensity Exercise Versus High-Intensity Interval Training to Recover Walking Post-Stroke

Finalized on 08-07-2020. Uploaded to ClinicalTrials.gov on 04-13-2021, prior to completion of data collection and prior to any outcome data analysis.

Overall Statistical Methods

SAS will be used for data analysis, and the study statistician will remain blinded to study group. Data related to baseline variables, intervention fidelity and concurrent outside interventions will be compared between groups using t-tests and χ^2 . If a baseline prognostic factor is found to differ between groups, it will be considered for inclusion as a covariate during hypothesis testing. The primary analysis will follow intent-to-treat methods and any missing data will be handled with the maximum likelihood method, assuming that patterns of missingness do not violate the missing at random assumption.¹ To test robustness of different ways to handle missing data, sensitivity analyses will be used.

Hypothesis Testing

Hypothesis 1: To test our primary hypothesis that, compared with 4 weeks of MAT, 4 weeks of HIT will elicit significantly greater improvement in the 6MWT distance, a general linear model will be used. In this model, we will use fixed effects for group (HIT, MAT), time (PRE, 4-WK, 8-WK, POST), [group x time], site (UC, KUMC, UD), [site x time], baseline speed category (<0.4 , ≥ 0.4 m/s), and [baseline speed category x time] with an unstructured covariance matrix. This hypothesis will be tested by the significance of the [group x time] contrast from the PRE to 4-WK for the 6MWT at $\alpha=0.05$. Secondary outcomes will be tested separately using this same model to identify the most sensitive measures to carry forward into future studies.² The Benjamini-Hochberg procedure³ will be used to control the false discovery rate for the secondary

outcomes, which include: comfortable gait speed, fast gait speed, VO_2 at the ventilatory threshold and the PROMIS-Fatigue Scale total score.

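### Secondary AEs are compared only per training session; a comparison over observed time should stand beside it for any AE, unrelated AEs and falls

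*Protocol*

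**What the plan says.** Protocol section E.2, Safety Data Analysis, compares SAEs as yes/no per participant. It then sends all secondary safety outcomes, meaning the AE grades and categories, through the same logistic model "with [# AEs / # training sessions] as the dependent variable". The SAP's Safety Data Analysis covers SAEs only, so the protocol sentence is the whole plan for other AEs.

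The AE definition in the Data and Safety Monitoring Plan requires no causal link and is not confined to training: "This includes any adverse clinical change that occurs at any time following consent".

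The per-session model comes from the pilot trial. The footnote to Table 7 (section G.1) reads "AE odds ratios are from logistic regression modeling of no. of AEs / no. of sessions per participant".

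In this trial, "Participants in both groups will be asked to perform 36 training sessions over approximately 12 weeks". Attendance is a fidelity measure ("Adherence will be measured by the number of training sessions attended"). The protocol says that "data on intervention fidelity and concurrent outside interventions will be compared between groups with t-tests", and the SAP's Overall Statistical Methods repeats this.

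**The concern.** For many AEs the numerator runs on calendar time and the denominator on attendance. A fall at home on a non-training day can happen whether or not that week's sessions were attended. For such events time under observation is the exposure, and dividing by sessions inflates the rate in the arm that attends less.

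The protocol expects similar non-serious AE rates in the two arms. With unequal attendance and continued follow-up, the arm that attends less would look worse on unrelated AEs with no true difference. A true excess in the arm that attends more would be diluted by the same factor. Comparing attendance between arms would reveal the gap but would not correct the AE comparison.

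**Working it through.** **Reproducing the pilot figures.** Table 7 has 141 HIT sessions (13 participants) and 60 MAT sessions (5 participants). With OR = [a/(141−a)] / [b/(60−b)] and a Wald interval:
- any AE, 21 v 8: 1.14 (0.47 to 2.73)
- related, 13 v 4: 1.42 (0.44 to 4.55)
- unrelated, 8 v 4: 0.84 (0.24 to 2.91)

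All three match Table 7. Sessions therefore act as binomial trials, and the intervals match a model with no overdispersion term.

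**Share of AEs not driven by training.** Unrelated AEs were 8 + 4 = 12 of 29. Falls were 0 related and 3 unrelated.

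**Size of the shift.** Let both arms have the same true rate L per participant over 12 weeks, with full follow-up. The per-session rate is L / (36 × attendance), so the rate ratio is the inverse attendance ratio. The attendance figures are assumptions; the documents give none for this trial. L = 2.0 is the pilot rate of unrelated AEs (12/18 per 4 weeks × 3), and L = 0.5 is the pilot fall rate (3/18 × 3, from only 3 events). At L = 2.0 the 95% arm has 2/34.2 = 0.0585 per session, odds 0.0621. The 85% arm has 2/30.6 = 0.0654, odds 0.0699, giving OR 1.13. False-difference rates are from simulation with 25 per arm and Poisson counts (nominal 5%).

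| Attendance | Rate ratio | OR at L = 2.0 | False difference, L = 0.5 | L = 1.0 | L = 2.0 |
|---|---|---|---|---|---|
| 85 v 95% | 1.12 | 1.13 | about 5% | 7% | 9% |
| 80 v 95% | 1.19 | 1.20 | about 7% | 10% | 15% |
| 70 v 95% | 1.36 | 1.39 | about 11% | 20% | 36% |

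Over observed time the ratio is 1.00 throughout. Without any overdispersion term the time-based test at L = 2.0 stays just under 5%, so the excess in the table comes from the denominator.

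**Precision.** The 95% interval spans a factor of exp(1.96 × √(2/events per arm)) either way. That is 2.2 at the fall rate (12.5 events per arm) and 1.5 at L = 2.0 (50 events).

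**Mixed categories.** Related AEs at full attendance: 17/201 × 36 = 3.04 per 12 weeks. For any AE at 85 v 95%, the per-time ratio is (3.04 × 0.85 + 2) / (3.04 × 0.95 + 2) = 4.58/4.89 = 0.94. The per-session OR, from 4.58/30.6 v 4.89/34.2, is 1.06. At 80% the pair is 0.91 and 1.09; at 70%, 0.84 and 1.17. For joint/muscle pain (12 related, 4 unrelated), 12/201 × 36 = 2.15 and 4/18 × 3 = 0.67. At 80 v 95% the rate ratio is 0.88 per time and 1.05 per session.

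**Detection.** AEs are asked about at study visits, so missed sessions may mean missed AEs. If half of the AEs in missed-session time went unrecorded, the unrelated-AE ratio at 85 / 80 / 70% would be 0.95 / 0.92 / 0.87 per time and 1.06 / 1.10 / 1.18 per session. For example, (1 − 0.5 × 0.15) / (1 − 0.5 × 0.05) = 0.95. Per time becomes the more biased of the two above about 53 to 55% unrecorded.

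**Clustering.** Seventeen related AEs in 18 participants would affect 18 × (1 − e^(−17/18)) = 11.0 participants under a Poisson model. Seven were affected. Unrelated AEs show no such pattern (9 affected, 8.8 expected).

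**The case against.** The strongest objection is that nothing shows the condition will arise. A reader might infer from the pilot's session counts that HIT participants skip sessions. The documents do not support that reading. MAT completed 60 of 60 sessions. HIT completed 141 of 13 × 12 = 156, but Table 1 (section C) reports 11 HIT participants against 13 in Table 7. Eleven completers account for 132 sessions, leaving 9 for the other two. That fits dropout, and dropout that also ends follow-up causes no shift. This objection stands, and it limits the point to a conditional one.

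A reader might also conclude that per session is the wrong scale and should give way to time. That does not follow either. Per session is right for training-related AEs, 17 of 29 in the pilot. For joint/muscle pain the per-time ratio departs further from 1 than the per-session ratio, because the arm that trains less has fewer training AEs. Visit-based questioning can also bias the per-time result.

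Finally, if the trial report follows Table 7's layout, a reader could compute AEs per participant unaided. That is fair, but the plan does not commit to that layout.

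**Conclusion.** The point holds as a modest, conditional weakness in the secondary safety analysis. All AE grades and categories have one denominator, and it does not suit events that training does not drive. If attendance differs while follow-up continues, the unrelated-AE ratio moves by about the inverse attendance ratio, and lower MAT attendance would make HIT look safer. A 10-point gap is minor: a ratio of 1.12, with false differences of about 5 to 9%. At the fall rate the shift is small beside the interval. Only a gap near 25 points with all unrelated AEs pooled gives a serious error, about 36%.

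These sizes rest on assumed attendance, event rates from 18 pilot participants, Poisson counts, full follow-up, and no adjustment for site or speed stratum. SAEs are analysed per participant and are unaffected, as is efficacy. The case for acting is that the change is cheap and is best fixed before attendance by arm is known.

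**What to change.** Keep the per-session model for all grades and categories. Add to the Safety Data Analysis sections of both the protocol and the SAP:

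> For any AE, for AEs rated unrelated to the intervention and for falls, AE counts from randomisation to 12WK or last contact are also compared between arms. The count model includes arm, site and baseline speed stratum, with log observed time as offset. If events are too few to fit it, the number of participants with at least one event is compared. Participants affected, total AEs, sessions attended and observed time are reported by arm. Both the per-session and the per-time models allow for overdispersion from repeated AEs within a participant.

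State that neither result replaces the other: per session addresses training-related AEs, and per time addresses burden per participant. State also that the per-time result may under-count AEs in an arm that misses sessions. The any-AE comparison does not depend on the relatedness rating, for which the documents state no blinding.

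The cost is wording, minor programming and somewhat wider intervals. Last-contact dates are needed; if they are not recorded, AEs per randomised participant can be used instead.

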Statistical Analysis Plan

NCT03760016

Moderate-Intensity Exercise Versus High-Intensity Interval Training to Recover Walking Post-Stroke

Finalized on 08-07-2020. Uploaded to ClinicalTrials.gov on 04-13-2021, prior to completion of data collection and prior to any outcome data analysis.

Overall Statistical Methods

SAS will be used for data analysis, and the study statistician will remain blinded to study group. Data related to baseline variables, intervention fidelity and concurrent outside interventions will be compared between groups using t-tests and χ^2 . If a baseline prognostic factor is found to differ between groups, it will be considered for inclusion as a covariate during hypothesis testing. The primary analysis will follow intent-to-treat methods and any missing data will be handled with the maximum likelihood method, assuming that patterns of missingness do not violate the missing at random assumption.¹ To test robustness of different ways to handle missing data, sensitivity analyses will be used.

Hypothesis Testing

Hypothesis 1: To test our primary hypothesis that, compared with 4 weeks of MAT, 4 weeks of HIT will elicit significantly greater improvement in the 6MWT distance, a general linear model will be used. In this model, we will use fixed effects for group (HIT, MAT), time (PRE, 4-WK, 8-WK, POST), [group x time], site (UC, KUMC, UD), [site x time], baseline speed category (<0.4 , ≥ 0.4 m/s), and [baseline speed category x time] with an unstructured covariance matrix. This hypothesis will be tested by the significance of the [group x time] contrast from the PRE to 4-WK for the 6MWT at $\alpha=0.05$. Secondary outcomes will be tested separately using this same model to identify the most sensitive measures to carry forward into future studies.² The Benjamini-Hochberg procedure³ will be used to control the false discovery rate for the secondary

outcomes, which include: comfortable gait speed, fast gait speed, VO_2 at the ventilatory threshold and the PROMIS-Fatigue Scale total score.

Hypothesis 2: To test the hypothesis that, compared with 4 and 8 weeks of HIT, 12 weeks of HIT will elicit significantly greater improvements in walking capacity and increased benefit over MAT, the same general linear model described above will be used. The hypothesis that 12 weeks of HIT will elicit greater improvements in primary and secondary outcomes compared to 4 and 8 weeks of HIT will be tested by the significance of the respective time contrasts within the HIT group. The hypothesis that HIT will elicit significantly greater improvements in primary and secondary outcomes from PRE to 8-WK and PRE to POST compared to MAT will be tested by the significance of the respective [group x time] contrasts. False discovery rate control will be applied for secondary outcomes.³

Prognostic Factor Testing

We will also test for baseline cofactors that may influence a stroke survivor's response to the interventions in this study. To do this, we will utilize a multivariate prognostic model that includes comfortable gait speed, lower extremity Fugl-Meyer motor scores, and scores on the Activities-Specific Balance Confidence Scale. These measures were selected based on previous studies suggesting that comfortable gait speed,⁴⁻⁹ lower limb Fugl-Meyer motor scores,⁹⁻¹¹ and balance abilities¹² may influence response to gait rehabilitation interventions in individuals with chronic stroke. Other potential cofactors will also be explored to inform future studies.

Safety Data Analysis

We expect a similar rate of non-serious adverse events (AEs) between HIT and MAT (e.g. temporary exercise-related soreness and fatigue), without any study-related serious AEs. In the unexpected event of one or more serious adverse events (SAE), the SAE rate will be compared between groups to confirm that there is no significant difference in major safety risk between HIT and MAT. A logistic regression model will be used for this analysis with SAE (yes/no) as the dependent variable and fixed effects for group, site, and baseline gait speed category. If there are SAE(s) in one group only, a continuity correction (0.5 SAEs added to each group) will still allow the odds ratio to be calculated.¹³

References

2. Dobkin BH. Progressive Staging of Pilot Studies to Improve Phase III Trials for Motor Interventions. *Neurorehabil Neural Repair*. 2009;23(3):197-206.
